1. SPECIFIC AIMS

The proposed pilot study is an exploratory implementation and mixed methods evaluation of self-guided repetitive art-making to assess the impact of this artistic practice on 1) self-reported pain levels, 2) self-reported mood states including anxiety and depression, and 3) self-reported feelings of connection for patients living with chronic pain and opioid use disorder (OUD) or documented misuse of opioids. A secondary research focus will be to assess whether viewing art made by patients with chronic pain and OUD/opioid misuse diminishes stigma towards these populations for the broader population.

Aim 1 (Acceptability): Develop three (3) self-guided repetitive artmaking kits for patients with chronic pain and OUD/opioid misuse to use on their own, with instructions in English and Spanish, and train the patients on the use of these artmaking kits through three (3) in-person workshops in English and Spanish. *Hypothesis 1: Simple art kits that offer repetitive artmaking practices will be acceptable for and interesting to patients with chronic pain and OUD/opioid misuse.* Acceptability will be measured by whether patients complete the pre- and post-survey and/or whether they report to the Study Coordinator during monthly check-ins that they have engaged with the art kit(s). At least 80% of patients will report using an art kit on their own (via self-report on surveys, to be supplemented by Study Coordinator text check-ins and storytelling data for patients who participate in the final showcase event). We will ask brief questions at the workshops to assess patients' previous experience with art and openness to mindfulness activities, along with a brief demographic questionnaire, to provide a baseline.

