Check-in Texts & Calls	The Study Coordinator will text all patients one (1) month after the in-person workshop and every one (1) month thereafter for a total of four (4) connection points to assess any barriers to at-home engagement; for those patients who do not respond to texts, the Study Coordinator will complete phone calls and document in Redcap	
 • Question asking whether patients used the art kits in the past month • Documentation of any barriers • Brief qualitative data
Meaning Making Session	All patients will be invited to join a two-hour virtual meaning making session	
 • Rich qualitative data of their experience of the art kits and solo repetitive artmaking
Exhibit	Exhibit viewers (laypersons) will complete an online post-survey via QR code that captures reactions before/after viewing the exhibit	
 • Short set of stigma questions to be developed

Most data will be collected online, via an online survey that automatically populates into a password protected spreadsheet. The Patient Advocate or Study Coordinator will collect all paper surveys during routine treatment at [name] and provide them to the Study Coordinator, who will clean and manually input the data.

Data Analysis:

Analysis will be conducted through a mixed-methods approach. Quantitative analysis to test hypotheses 2-5 will be led by [name], Biostatistician, who will report changes from pre- and post-surveys on all the measures provided to patients and exhibit viewers. For bivariate analyses, he will use paired t-tests. For multivariate analyses, he will employ control variables from baseline, such as demographic variables, and conduct linear regressions. Qualitative analysis to test hypotheses 1-5 will be led by the co-PI, who will code all qualitative data collected from patients (open-ended questions in all surveys, transcript from the meaning making session) to

surface themes that can provide phenomenological or experiential data. Drs. [name] and the co-PIs will collaborate to develop a final report that includes both quantitative and qualitative data.

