4. STUDY POPULATION

Individuals will be eligible to participate in the pilot study if they:

1. Experience chronic pain
2. Have received medication for OUD in the past 30 days
3. Are aged 18 or older
4. Are fluent in English and/or Spanish

Eligibility screening to be led by the Study Coordinator will include:

1. Chronic pain screening via the first three questions of the BPI Reduced Minus Peg Questions 8-item questionnaire
2. OUD/opioid misuse assessment via the Modified Addiction Severity Index question about recent opioid use

Patients will be enrolled into the study until a total of approximately 40 have completed the in-person art workshops; due to the nature of this community and the high level of attrition, we plan to over-enroll the workshops and as a result may have more than 40 participations at the conclusion.

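### The check-ins ask about kit use only in the past month, so use in a missed or late month can go unrecorded for patients who leave no other evidence of it

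*Combined protocol and SAP*

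**What the plan says.** Section 1, Aim 1, sets the target: "At least 80% of patients will report using an art kit on their own". It names the sources as "via self-report on surveys, to be supplemented by Study Coordinator text check-ins and storytelling data", the last of these only for patients who join the final showcase. The same paragraph gives the rule: "Acceptability will be measured by whether patients complete the pre- and post-survey and/or whether they report to the Study Coordinator during monthly check-ins". Surveys therefore come first, and a check-in report can also establish use.

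The Data Collection table in section 3 starts the check-ins one month after the workshop and continues them "every one (1) month thereafter for a total of four (4) connection points". The use item listed is "Question asking whether patients used the art kits in the past month". There is a back-up: "for those patients who do not respond to texts, the Study Coordinator will complete phone calls and document in Redcap". The table lists no item on use since the workshop and no end-of-study use question. Separately, patients are paid for up to four at-home survey pairs over the four months.

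Neither section says who forms the denominator of the 80%, or how to classify a patient with missing check-ins.

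**The concern.** Four one-month windows cover the four-month period only if every contact succeeds and is on time. If the month-1 contact fails, the month-2 question does not reach back to month 1. If a patient is reached two weeks late, the first two weeks of that interval fall outside the question.

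The patients affected are those who used a kit but returned no survey, and they are the group the check-ins add to the measure. Such a patient could truthfully answer no at every completed contact. With about 40 patients, a few of these can move the observed share across 80%.

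**Working it through.** **Inputs from the documents.** Target 80%; about 40 workshop completers; four monthly contacts; past-month look-back. The 80% is a bare target with no calculation behind it. With exactly 40 patients it means 0.80 × 40 = 32 users.

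**Assumptions (the documents give no rates).**
- T, true share of users: 85%.
- m, chance that a contact is missed: 10% to 40%, independent between months.
- k, months in which a user is active: 1 or 2, equally likely to be any of the four.
- s, share of users returning at least one at-home survey: 0 to 80%.
- Storytelling data are ignored, and a patient with no recorded use counts as a non-user.

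**Formula.** Observed share = T × (1 − L × (1 − s)), where L is the chance that the check-ins miss all of a user's use.
- Past-month item: L = m^k.
- Since-workshop item: L = the average of m^(5 − first month of use). An item reaching back to the last completed contact gives the same L.

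**One month of use, m = 0.20.**
- Past-month: L = 0.20.
- Since-workshop: L = (0.0016 + 0.008 + 0.04 + 0.20)/4 = 0.0624.
- s = 0.5: 0.85 × (1 − 0.10) = 76.5%, against 0.85 × (1 − 0.0312) = 82.3%.
- s = 0.8: 0.85 × (1 − 0.04) = 81.6%, against 0.85 × (1 − 0.0125) = 83.9%.

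The binomial chance of reaching 32 of 40 is 0.865 with no loss. With s = 0.5 it is 0.380 against 0.734; with s = 0.8 it is 0.691 against 0.817.

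**Two months of use, m = 0.20, s = 0.8.**
- Past-month: L = 0.04, giving 84.3%.
- Since-workshop: of the six possible pairs of months, three start in month 1, two in month 2 and one in month 3. L = (3 × 0.0016 + 2 × 0.008 + 0.04)/6 = 0.0101, giving 84.8%.
- The gap is about 0.5 points.

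**Range over m (one month of use; past-month against since-workshop).**

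| m | s = 0.5 | s = 0.8 |
|---|---|---|
| 10% | 80.75% vs 83.8% | 83.3% vs 84.5% |
| 20% | 76.5% vs 82.3% | 81.6% vs 83.9% |
| 30% | 72.25% vs 80.5% | 79.9% vs 83.2% |
| 40% | 68.0% vs 78.1% | 78.2% vs 82.2% |

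With no surveys at all, the past-month shortfall from the true 85% would be 8.5 to 34 points over the same range of m.

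**Direction.** Suppose instead that unresolved patients are dropped, and a non-user counts only when all four contacts are complete. At m = 0.20 and s = 0, the past-month share is 0.68/(0.68 + 0.15 × 0.8^4) = 0.68/0.741 = 91.7%, above the true 85%. With the since-workshop item, a completed last contact settles a non-user, and the share is 0.797/(0.797 + 0.15 × 0.8) = 86.9%.

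**The case against.** The strongest reply is that the check-ins are only a supplement. A paid survey pair, a yes in any other month or storytelling data can each show use. Paper surveys are collected during routine clinic treatment, so that source does not depend on phone contact, and unanswered texts are followed by calls. All of this stands. A reader might infer that a missed contact loses the use for good; the documents do not support that.

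A reader might also take "due to the nature of this community and the high level of attrition" as evidence that missed check-ins will be the normal case. In section 4 that phrase justifies over-enrolling the workshops. It gives no rate for the check-ins, and none can be drawn from it.

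Three further points carry weight:
- The table may summarise the item rather than give its script, and the same row collects brief qualitative data in which earlier use could be noted. Still, no cumulative item is listed, and no rule says that such notes count.
- The row's stated purpose is to find barriers to home engagement, which a fixed monthly window serves well. That is a reason to keep the item and add to it.
- Missed contacts probably cluster in the same patients. Independence then flatters the new question, since it recovers nothing when no later contact succeeds.

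**Conclusion.** The gap is real but narrow. Use in a missed or late month escapes the later check-ins, and it is lost to the Aim 1 measure only for patients with no at-home survey, no yes at another check-in and no storytelling data.

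A reader might infer that the 80% share must be understated, or that the target would be failed for this reason. Neither follows. The direction depends on a denominator and missing-data rule that the plan does not state. The size depends on assumed rates of contact, survey return and use: with 20% of contacts missed and 85% true use, the wording makes a difference of 5.8 points (one month of use, 50% returning surveys), 2.3 points (one month, 80%) or about 0.5 points (two months, 80%). For scale, the standard error of an 85% share in 40 patients is √(0.85 × 0.15/40), about 5.6 points.

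This is an exploratory pilot, and the Data Analysis section assigns quantitative testing to hypotheses 2 to 5 only, so no formal test of Hypothesis 1 is affected. Severity is minor.

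**What to change.** - Keep the past-month item, which serves the monthly record of barriers.
- Add to each check-in: *Have you used a kit at home at any time since the workshop (or since our last completed contact)?*
- Record the date of each completed contact in REDCap.
- State in Aim 1 that a patient is a user if any completed contact or at-home survey reports use, with all workshop completers as the denominator. Say also whether storytelling data alone can establish use.

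The cost is one extra question, one date field and slightly longer recall after a missed contact. The change cannot recover use that occurs after a patient's last completed contact, including month-4 use when the fourth contact is missed.

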4. STUDY POPULATION

Individuals will be eligible to participate in the pilot study if they:

1. Experience chronic pain
2. Have received medication for OUD in the past 30 days
3. Are aged 18 or older
4. Are fluent in English and/or Spanish

Eligibility screening to be led by the Study Coordinator will include:

1. Chronic pain screening via the first three questions of the BPI Reduced Minus Peg Questions 8-item questionnaire
2. OUD/opioid misuse assessment via the Modified Addiction Severity Index question about recent opioid use

Patients will be enrolled into the study until a total of approximately 40 have completed the in-person art workshops; due to the nature of this community and the high level of attrition, we plan to over-enroll the workshops and as a result may have more than 40 participations at the conclusion.

5. PARTICIPANT RECRUITMENT

Patients will be recruited by the Study Coordinator and Patient Advocate from [name]. Patient Advocates have existing trusted relationships with clients at this methadone clinic site. The Study Coordinator will coordinate with the Patient Advocate's existing schedule to they can collaborate on talking to patients, sharing information about the study, and in the case of the Study Coordinator, assessing eligibility. Information about the study will additionally be shared in the form of flyers posted around the recruitment site, and the co-PIs will present to all staff during scheduled staff meetings to orient the staff to the project and request direct referrals.

6. INFORMED CONSENT

Informed consent will be conducted by the Study Coordinator as follows: all potential patients will complete a brief oral consent and then complete the eligibility screener. This process can take place in-person in a private room at [name] or over the phone in the case of patients who wish to be screened at a time of their choosing as opposed to when they encounter the study team. If eligible, the Study Coordinator will explain the study and any risks and benefits, and obtain written informed consent.

Remuneration:

Patients will receive \$50 for participating in the in-person workshop and will be incentivized to use the art kits at home and complete pre- and post-testing for up to four times with \$20 each time. Further, all patients will be invited to participate in a meaning making session to capture qualitative feedback on the feasibility of the project; if they attend, they will be compensated \$50 for their participation. Patients will be compensated through a Clincard in their name. These cards include no information that link them to the study or indicate that this compensation is related to a study.

7. RISK/BENEFIT TO PARTICIPANTS

The study protocol asks that patients reflect on their levels of pain, depression, anxiety, and social connection and as such could bring these experiences to the forefront of patients' minds during study activities and result in discomfort. There is also a small risk of loss of confidentiality, as patients will be recruited in a community setting – the [name] methadone clinic. To address confidentiality, we will remove any names used in the meaning making session during the transcription process and will enclose all written information about the study that is included in the art kits so that they are not immediately viewable by third parties. Audio recording of the meaning making session will be stored in a password protected folder on a password protected computer and destroyed once it has been transcribed. Patients will further be informed that they can refuse to answer any question if it makes them uncomfortable, and will be reminded that their participation is wholly voluntary.

Patients participating in groups and home practice may benefit from potential improvements in pain, OUD, and mental health symptoms. They will derive no specific benefits from completing questionnaires and participating in qualitative interviews.

8. DATA QUALITY CONTROL AND DATABASE MANAGEMENT

To protect confidentiality, each patient will be assigned an alphanumeric ID. The spreadsheet listing patient names and their associated ID, along with workshop attendance forms which will also include patient names, will be saved in a password protected folder separate from all other materials. During the data cleaning process of the pre- and post-surveys from both the workshops and the at-home data collection, the Study Coordinator will replace patient names with their respective ID. The audio recording of the meaning making session will be stored in a password protected folder on a password protected computer and destroyed once the session has been transcribed. All names and other identifying elements will be removed from the meaning making data during the transcription process.

CITATIONS

1. Yong, R. J., Mullins, P. M., & Bhattacharyya N. (2002). Prevalence of chronic pain among adults in the United States. *Pain*, 163(2), e328-e332.
2. Rikard, S. M., Strahan, A. E., Schmit, K. M., & Guy Jr., G. P. (2023). Chronic pain among adults – United States 2019-2021. *Weekly*, 72(15), 379-385.
3. Lerman, S. F., Rudich, Z., Brill, S., Shalev, H., & Shahar, G. (2015). Longitudinal associations between depression, anxiety, pain, and pain-related disability in chronic pain patients. *Psychosomatic Medicine*, 77(3) 333-341.
5. Lerman, S. F., Rudich, Z., Brill, S., Shalev, H., & Shahar, G. (2015). Longitudinal associations between depression, anxiety, pain, and pain-related disability in chronic pain patients. *Psychosomatic Medicine*, 77(3) 333-341.
6. Allen, S. F., Gilbody, S., Atkin, K., & van der Feltz-Cornelis, C. (2020). The associations between loneliness social exclusion and pain in the general population. A =502,528 cross-sectional UK biobank study. *J Psychiatr Res*, 130, 68-74.

8. Angheluta A-M., & Lee, B. L. (2011). Art therapy for chronic pain: Applications and future directions. *Canadian Journal of Counselling and Psychotherapy*, 45(2), 112-131.

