Aim 2 (Efficacy): Evaluate whether the self-guided repetitive artmaking kits significantly impact patients' self-reported experiences of pain, mood (inclusive of depression and anxiety), and social isolation. *Hypothesis 2: Repetitive artmaking will reduce experiences of pain for patients with both chronic pain and OUD/opioid misuse.* Acceptance criteria: Significant pain reduction during artmaking practice as captured using the first three questions of the BPI Reduced Minus Peg Questions 8-item questionnaire (attached) – questions one and two will be only asked in the pre-survey as these questions ask about pain over the last week and will therefore not change before and after a solo artmaking experience. We also propose to have patients complete the 6-item Pain Catastrophizing Questionnaire (attached) during the in-person workshop to gain an understanding about patients' experiences of pain. This data will be supplemented with qualitative data from the meaning making session and storytelling content, for those who participate. *Hypothesis 3: Repetitive artmaking will reduce depression and anxiety and improve mood for patients with chronic pain and OUD/opioid misuse.* Significance improvements in mood (anxiety and depression) during artmaking practice as captured using single survey questions asking patients to rate their current experiences of anxiety and depression. This data will be supplemented with qualitative data from the meaning making session and storytelling content, for those who participate. *Hypothesis 4: Supporting patients with chronic pain and OUD/opioid misuse in making art will result in higher ratings of social connectivity.* Significant improvement in social connectivity during artmaking practice as captured using the IOS-CC (attached). *Hypothesis 5: Repetitive artmaking will reduce opioid misuse in patients.* Any reduction in non-prescribed opioid use as captured by a question asking patients if they have used non-prescribed opioids in the past 24 hours (modified from the Addiction Severity Index question about recent opioid use) as both a measure of opioid use in connection with artmaking and we will be evaluating patients' opioid use over the course of the study, and a question asking patients to share how high they are at the time of the survey (from the Modified DFAQ-CU Inventory but focusing on opioids not cannabis). This

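### Surveys that ask about non-prescribed opioid use appear to carry patients' names until data cleaning, and the paper ones are handed in at the methadone clinic; the study ID should be on the forms from the start and paper returns sealed.

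*Combined protocol and SAP*

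**What the plan says.** **Identifiers.** Section 8 (Data Quality Control and Database Management) states that "each patient will be assigned an alphanumeric ID", with the list linking names to IDs kept in a separate protected folder. The ID reaches the survey data only at the cleaning stage. For workshop and home surveys alike, the plan is that "the Study Coordinator will replace patient names with their respective ID" at that point.

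**Content.** The data collection table in Section 3 puts the items on current and recent unprescribed opioid use (pre-survey) and on feeling high (pre- and post-survey) on the workshop survey and on all four home surveys.

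**Return.** Section 3 also says "The Patient Advocate or Study Coordinator will collect all paper surveys during routine treatment" at the recruitment site, which the Section 3 overview and Section 5 identify as a methadone clinic. Section 5 adds that Patient Advocates already have relationships with clients there.

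**Mode.** The text below the table says "Most data will be collected online, via an online survey that automatically populates into a password protected spreadsheet". The table itself lists paper for every home session, while the At-Home Artmaking paragraph says that links are sent as well.

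**Use of the data.** The criterion for Hypothesis 5 in Section 1 is "Any reduction in non-prescribed opioid use as captured by a question asking patients if they have used non-prescribed opioids in the past 24 hours", together with a rating of how high the patient feels.

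**The concern.** A form that joins a patient's name to an admission of non-prescribed opioid use is among the most sensitive records in this study. If it is mislaid, or read by someone who does not need to see it, the harm falls on the patient. Section 7 concedes "There is also a small risk of loss of confidentiality" but ties it to recruitment in a community setting and does not mention named opioid answers.

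There is also a measurement issue. Hypothesis 5 rests on self-report, and the plan describes no objective measure of use. A patient who hands a named form to someone known from the treating clinic has an evident reason to understate use.

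**Working it through.** The plan states no figure to reproduce. The check is first a reading of the sections side by side, then simple arithmetic under assumed values.

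**1. Are the raw surveys named?** Section 8 describes names being replaced during cleaning, for both workshop and home surveys. There is nothing to replace unless responses arrive with names. No name field is described and the forms are not in the text, so this is an inference, though the natural one. The replacement step is not limited to paper, so online records appear to be affected too.

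**2. Do the stated safeguards cover the interval from completion to cleaning?**

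| Safeguard | Where | What it leaves open |
|---|---|---|
| Names stay within the core team | Section 3, overview | The core team includes the Patient Advocate, who may collect the forms |
| Survey material placed inside the kit, out of view | Section 3; Section 7 | Helps while the form is in the kit, not at hand-in |
| Separate list of names and IDs | Section 8 | Protects little while the completed form itself carries the name |
| Right to decline any question | Section 7 | Lets a patient avoid disclosure, but does not protect an answer once given |

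None covers the interval. No sealed return and no pre-labelled form is described.

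**3. What could under-reporting do to Hypothesis 5?** The 24-hour item is asked only before each session, so a change in it can be seen only between sessions. Let *p* be true 24-hour use, and let *s0* and *s1* be the share of users who admit it at an earlier and a later survey. All values below are assumptions.

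*Constant reporting (s0 = s1 = s).* Observed fall = *s* × true fall. For a true fall of 10 points:
- s = 0.8: 0.8 × 10 = 8 points
- s = 0.6: 0.6 × 10 = 6 points

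*Reporting that differs, with no true change.* Observed fall = *p* × (*s0* − *s1*). To express this against the criterion, take X0 ~ Bin(40, *p·s0*) and X1 ~ Bin(40, *p·s1*). The chance of any observed reduction is then the sum over x of P(X0 = x) × P(X1 ≤ x − 1).

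| p | s0 → s1 | Observed fall | Chance of any reduction |
|---|---|---|---|
| 0.2 | 1 → 1 | 0 | 0.444 |
| 0.2 | 0.9 → 0.7 | 4 points | 0.632 |
| 0.2 | 0.7 → 0.9 | −4 points | 0.260 |
| 0.4 | 1 → 1 | 0 | 0.455 |
| 0.4 | 0.9 → 0.7 | 8 points | 0.743 |
| 0.4 | 0.7 → 0.9 | −8 points | 0.186 |
| 0.6 | 1 → 1 | 0 | 0.455 |
| 0.6 | 0.9 → 0.7 | 12 points | 0.834 |
| 0.6 | 0.7 → 0.9 | −12 points | 0.116 |

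This treats the two surveys as independent and assumes that all 40 patients return both. In fact the same patients respond, home sessions are optional, and Section 4 expects high attrition. The table shows that the bias can go either way; it does not estimate its size.

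**The case against.** Several points count against making more of this, and most of them stand.

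- **Clinic hand-in concerns paper only.** Section 3 says most data are online. The share on paper is unknown because the table and the text disagree about home sessions.
- **Disclosure to treating clinicians is not shown.** A reader might infer that the clinic's treating staff read the answers. The documents do not say so: the collectors are study team members, and Section 5 describes the Patient Advocates' relationships as trusting, which could encourage candour. The Study Coordinator already asks about recent opioid use at screening (Section 4), so an ID hides little from that role. What remains is possible Patient Advocate access to open paper forms, forms that go astray, and named online records.
- **Named forms do not by themselves produce a spurious success on Hypothesis 5.** A reader might infer that patients would admit less on named home forms than at the workshop, so that reported use would fall with no real change. The documents do not support this. The replacement step covers workshop and home surveys alike, so naming is constant and would by itself be expected to attenuate a true change. A differential would have to come from the setting, and completing a survey at home could as plausibly raise candour as lower it.
- **The loose criterion is a separate weakness.** With full reporting and no true change, any reduction is still met with probability 0.444 to 0.455 in the illustration. Using IDs would not alter that.
- **Consent pages are not available.** Nothing can be concluded about what patients are told there.

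None of this closes the gap between completing a form and cleaning it.

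**Conclusion.** The point holds as a confidentiality weakness with a possible effect on data quality. It rests on one inference, that the forms carry names, and on the stated collection route for paper. The exposure is avoidable because the IDs already exist and the kits are handed out in person. Under-reporting of opioid use is a reasonable expectation, but nothing in the documents quantifies it. If constant, it attenuates Hypothesis 5; if it differs between workshop and home, it can bias the result in either direction. The case for change does not depend on any of the assumed rates. This is an inexpensive improvement that should be made, not a flaw that invalidates the study.

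**What to change.** - **Section 8:** state that every paper survey carries the pre-assigned study ID and no name, and that online surveys use ID-specific links without a name field. This includes the workshop QR code, which would have to lead to an ID-specific entry.
- **Section 3:** put return envelopes in each kit. Paper forms are handed in sealed, and only the Study Coordinator opens them. The Patient Advocate can still collect them. Payment is matched through the existing separate list of names and IDs.
- **Section 3:** reconcile the statement that most data are collected online with the table that lists paper for all home sessions, so that the extent of paper handling is known.
- **Section 7:** name opioid-use answers on surveys as a confidentiality risk and describe these measures.

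The cost is labels, envelopes, individual links and a few sentences of protocol text. The one practical burden is that kits must be labelled per patient before they are handed out. No endpoint, sample size or clinical procedure changes.
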